3.3. Treatments

The chemical name of niclosamide is 5-chloro-N-(2-chloro-4-nitrophenyl)-2-hydroxybenzamide. The IMPs are in the form of white yellowish oval 400-mg uncoated immediate-release (IR) tablets containing the active ingredient micronized niclosamide or a matched placebo.

Subjects who are able to comply with the oral treatment must take, for each administration, 1 tablet (400-mg niclosamide or placebo) TID for 14 days. Treatment may begin at any time of day; if only 1 or 2 doses are administered on Day 1, the planned total number of doses should be administered (42 total doses) and the final doses may be administered on Day 15. The total study duration for a subject will not be extended if the final dose occurs on Day 15 for this reason.

4. General Statistical Considerations

Continuous data will be described using descriptive statistics (i.e., number of subjects, mean, standard deviation, median, 25th percentile, 75th percentile, minimum, and maximum). Unless otherwise specified, minimum and maximum will be displayed to the same level of precision as reported. Mean and median will be displayed to one level of precision greater than the data collected. Standard deviation (SD) and standard error (SE) will be displayed to two levels of precision greater than the data collected. If the precision of the values being summarized are too large (e.g., 3 or more decimal places), then limit the precision to two decimal places and follow the rules previously stated above. If n=0, then display n and leave all other statistics blank. If n=1, then display “N/A” for SD and SE.

Categorical data will be described using the subject count and percentage in each category. When count data are presented, the percentage will be suppressed when the count is zero. A row denoted “Missing” will be included in count tabulations where specified on the shells to account for dropouts and missing values where applicable. The denominator for all percentages will be

the number of subjects in that treatment within the analysis set of interest, unless otherwise specified. Non-zero percentages will be rounded to one decimal place, except 100% will be displayed without any decimal places.

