8.1.1. Primary Analysis

The analysis of the primary efficacy endpoint, time to fecal viral RNA clearance, will be conducted on the EE set.

The number and percentages of subjects achieving and not achieving the first fecal viral RNA clearance will be summarized up to each post-first dose study visit (Days 4, 8, 15, 22, 29, 36, and 43) by treatment group. For each study visit, only subjects with available assessment at the visit or having a negative stool test before the visit will be included in the summary and counted in the denominator for the percentages.

A stratified log-rank test will be used to compare time to fecal viral RNA clearance between niclosamide and placebo treatment groups adjusting for stratification factors, age (<65 years or ≥65 years) and sex (female or male). The two-sided p-value will be reported. The estimate of the hazard ratio (niclosamide vs. placebo) and the associated 95% confidence interval (CI) will be obtained from a Cox Proportional Hazards model adjusting for stratification factors and will also be reported.

Kaplan-Meier curves with 95% CIs will be generated for the total population by treatment group. Summary statistics obtained from Kaplan-Meier estimates, including the median time to fecal viral clearance with corresponding 95% CI and the proportion of subjects achieving fecal viral clearance at 3, 7, 14, 21, 28, 35, and 42 days post first dose (Day 1), will be summarized by treatment group.

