8.2.1. Time to fecal viral RNA clearance assessed by RT-qPCR (Part 1)

The number of subjects with and without fecal viral RNA clearance assessed by RT-qPCR (as defined in [Section 8.1.](#)) will be summarized up to each post-first dose study visit (Days 4, 8, 15, 22, 29, 36, and 43) by treatment group. For each study visit, only subjects with available assessment at the visit or having a negative stool test before the visit will be included in the summary and counted in the denominator for the percentages.

8.2.2. Time from the first dose of study treatment to the first formed stool

Only subjects with loose or watery stool (Bristol Stool Scale Types 6-7) on Day 1 will be included in this analysis. This data was collected on the Diarrhea Clinical Assessment at Randomization eCRF.

Date of the earliest formed stool (followed by a non-watery stool) between study visits will be collected on the Diarrhea Clinical Assessment eCRF. A summary table will include the number and percentage of subjects achieving and not achieving the first formed stool (followed by a non-watery stool) up to each post-first dose study visit (Days 4, 8, 15, 22, 29, 36, and 43) by treatment group. For each study visit, only subjects with available assessment at the visit or having a formed stool test before the visit will be included in the summary and counted in the denominator for the percentages.

Time to the first formed stool is defined as the time in days from the first dose of study treatment to the first formed stool (followed by a non-watery stool). If subjects experienced a formed stool on the first day of treatment, time to first formed stool will be imputed as 0.5 days. Subjects without a first formed stool will be censored using the same rules as described for the primary efficacy endpoint in [Section 8.1.](#) Time to the first formed stool (followed by a non-watery stool) will be analyzed using the same time to event methods described for the analysis of the primary endpoint in [Section 8.1.1.](#)

8.2.3. Time from the first dose of study treatment to the last watery stool

Only subjects with loose or watery stool (Bristol Stool Scale Types 6-7) on Day 1 will be included in this analysis. This data was collected on the Diarrhea Clinical Assessment at Randomization eCRF.

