8.2.5. Time from first dose of study treatment to improvement of abdominal symptoms

Only subjects with abdominal symptom(s) on Day 1 will be included in this analysis.

The overall severity of abdominal symptoms and the date of assessment will be collected on the Diarrhea Clinical Assessment. A summary table of severity will include the number of subjects with an assessment available and the number and percentage of subjects within each severity category at each study visit (Baseline, Days 4, 8, 15, 22, 29, 36, and 43) by treatment group. The proportion of subjects with any improvement from baseline of abdominal symptoms will also be provided in the summary table by treatment group. Improvement of abdominal symptoms is defined as any severity reduction from baseline by at least one level (i.e., mild to normal, moderate to mild or normal, or severe to moderate or mild or normal).

Time to the first improvement of abdominal symptoms is defined as the time in days from the first dose of study treatment to the first improvement of abdominal symptoms. Subjects without improvement of abdominal symptoms will be censored using the same rules as described for the primary efficacy endpoint in [Section 8.1](#). Time to improvement of abdominal symptoms will be analyzed using the same time to event methods as described for the analysis of the primary endpoint in [Section 8.1.1](#).

8.2.6. Proportion of subjects with a negative stool test for SARS-CoV-2 on Day 1 who acquire SARS-CoV-2 in stool through Day 43

This analysis will be conducted on the FAS and include only all subjects with a negative stool test for SARS-CoV-2 on Day 1.

A summary table will include the number and percentage (proportion) of subjects acquiring SARS-CoV-2 by treatment group first overall after Day 1 through Day 43 visit, then for each post-first dose study visit (Days 4, 8, 15, 22, 29, 36, and 43). For each study visit, only subjects with available assessment at the visit or having a positive stool test before the visit will be included in the summary and counted in the denominator for the percentages.

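### By-visit percentages keep every earlier event but drop event-free subjects with no sample; in SAP 8.2.6 no Kaplan-Meier estimate corrects this, and two rows can disagree on the same event.

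*SAP*

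**What the plan says.** SAP 8.1.1 (Part 2 primary endpoint) plans a table of subjects who have and have not cleared up to each visit, in which "only subjects with available assessment at the visit or having a negative stool test before the visit will be included in the summary". The same section also plans Kaplan-Meier curves, the median, and "the proportion of subjects achieving fecal viral clearance at 3, 7, 14, 21, 28, 35, and 42 days post first dose".

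SAP 8.2.1 (Part 1 fecal clearance) repeats the denominator rule ("only subjects with available assessment at the visit or having a negative stool test before the visit"). It lists no other analysis.

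SAP 8.2.6 (Day 1-negative subjects who later acquire virus in stool) uses the mirror rule: "only subjects with available assessment at the visit or having a positive stool test before the visit". Its table reports acquisition "first overall after Day 1 through Day 43 visit, then for each post-first dose study visit". No time-to-event method is named.

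SAP 8.2.2, 8.2.3 and 8.3.6 use the same kind of rule, but each also refers to the time-to-event methods of 8.1.1.

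Two other provisions matter. SAP Section 4 sets the default denominator for percentages as "the number of subjects in that treatment within the analysis set of interest, unless otherwise specified". SAP 8.1 defines clearance as sustained, and holds subjects who die, or who are hospitalised and withdraw consent, without clearance as uncleared to Day 43.

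**The concern.** Under this rule, inclusion depends on the outcome. Once the qualifying test has occurred, a subject counts at every later visit, sampled or not. A subject without it counts only if sampled at that visit. Missing samples therefore remove only event-free subjects, and the cumulative percentage rises even if missingness is unrelated to outcome.

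The rule also sits badly with SAP 8.1 in two ways. A never-negative subject who dies vanishes from later rows of the table, while the time-to-event analysis holds that subject as uncleared. And any earlier negative test secures a place in the denominator, although clearance must be sustained. Of two uncleared subjects absent at Day 43, one with a transient negative is kept and one without is dropped.

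At stake is the descriptive reporting of a listed secondary endpoint. In 8.2.6 the Day 43 row and the overall row describe the same cumulative event on what appear to be different denominators, and a reader would have no means of choosing between them.

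**Working it through.** **Inputs from the documents.** Exponential clearance with medians of 21 days (placebo) and 10 days (niclosamide), 30 evaluable per arm, 40% stool positivity, 150 subjects in Part 2 (SAP 4.1); visits at 3, 7, 14, 21, 28, 35 and 42 days after first dose (SAP 8.1.1); Part 1 of about 9 subjects randomised 2:1 (SAP 3.1 and 4.2).

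**Assumed.** Missingness of 5% to 30%, unrelated to outcome, either as permanent dropout by Day 43 or as single missed visits. True acquisition of 10% to 30% by Day 43 at a constant rate, with an acquirer still positive at the next available sample.

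**The plan's own figure.** Simulating the SAP 4.1 assumptions gives power of 73.9% (alpha 0.05) and 83.5% (alpha 0.10), against the stated 74% and 83%. The clearance model is reproduced.

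**Formulas.** Let S(t) be the event-free proportion and f(j) the proportion whose event falls between visits j−1 and j.
- Dropout d by day 42: fraction still followed G(t) = (1 − d)^(t/42). Observed events E = Σ f(j)·G(t_j). Event-free and assessed at the last visit: A = S(42)·G(42).
- Missed visits at rate m: E = Σ f(j)·(1 − m^(number of visits from j to the last)). A = S(42)·(1 − m).
- Rule percentage = E/(E + A). Full-denominator percentage = E.

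**Clearance at Day 43.** S(42) is 0.5^(42/21) = 0.250 for placebo and 0.5^(42/10) = 0.054 for niclosamide, so true clearance is 75.0% and 94.6%.
- 20% dropout, placebo: E = 0.678, A = 0.250 × 0.8 = 0.200; rule 0.678/0.878 = 77.2%.
- 20% missed visits, placebo: E = 0.733, A = 0.200; rule 0.733/0.933 = 78.6%.

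| Missing | Placebo, rule (dropout / missed visits) | Niclosamide, rule (dropout / missed visits) |
|---|---|---|
| 5% | 75.5 / 75.9 | 94.7 / 94.8 |
| 10% | 76.1 / 76.7 | 94.9 / 95.1 |
| 20% | 77.2 / 78.6 | 95.3 / 95.6 |
| 30% | 78.5 / 80.4 | 95.6 / 96.0 |

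Kaplan-Meier returns 74.8% to 75.7% and 94.5% to 95.0% at 10% to 30% missing, close to the truth. If all of a 20% dropout were deaths or hospitalised withdrawals, the placebo row would still read 77.2%, while Kaplan-Meier under the censoring in SAP 8.1 would read 68.0%.

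**New stool infection (8.2.6).** Day 1-negative subjects in Part 2: 150 × (1 − 0.40) = 90, about 45 per arm. With true acquisition 20%, S(42) = 0.80.
- 20% dropout: E = 0.177, A = 0.80 × 0.8 = 0.64. Day 43 row 0.177/0.817 = 21.7%; full denominator 17.7%.
- 20% missed visits: E = 0.192, A = 0.64. Day 43 row 0.192/0.832 = 23.1%; full denominator 19.2%.

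| True | Missing | Day 43 row (dropout / missed visits) | Full denominator (dropout / missed visits) |
|---|---|---|---|
| 20% | 10% | 20.8 / 21.5 | 18.9 / 19.7 |
| 20% | 20% | 21.7 / 23.1 | 17.7 / 19.2 |
| 20% | 30% | 22.7 / 25.0 | 16.5 / 18.7 |
| 10% | 20% | 10.9 / 11.8 | 8.8 / 9.6 |
| 30% | 20% | 32.2 / 34.0 | 26.6 / 28.9 |

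Under dropout, Kaplan-Meier recovers the truth. At visit j the risk set is S(t_{j−1})·G(t_j) and the events are f(j)·G(t_j). The ratio is 1 − S(t_j)/S(t_{j−1}), and the product over visits is S(42).

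**Part 1 (8.2.1).** Nine subjects give 6 active and 3 placebo; at 40% positivity 2.4 and 1.2 are evaluable, 3.6 in all. The chance of no evaluable placebo subject is 0.6³ = 22%.

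**All-subjects denominator as a remedy.** At 20% dropout it reads 67.8% (placebo) and 87.5% (niclosamide), errors of −7.2 and −7.1 points, against +2.2 and +0.7 under the rule.

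**The case against.** The strongest reply is that little depends on this table. SAP 8.1.1 gives Kaplan-Meier proportions at the same seven time points, and the log-rank test, hazard ratio and median do not use the by-visit denominator. That stands, and it extends to 8.2.2, 8.2.3 and 8.3.6. In Part 1 the endpoint is descriptive, subject listings are planned, and a Kaplan-Meier curve on one or two placebo subjects would settle nothing. That stands too.

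Three stronger readings are tempting, and the documents do not support them.
- **New infection is overstated throughout.** The visit rule in 8.2.6 is worded for each study visit. The overall row therefore appears to fall under the Section 4 default, where it errs low. A figure such as 0.20/(0.20 + 0.80 × 0.80) = 23.8% assumes that every acquirer is observed; when missingness applies to everyone, dropout gives 21.7%.
- **The rule always inflates the arm with more non-clearers, or favours niclosamide.** At Day 43 placebo is inflated more, and the 19.6-point difference shrinks to 18.0 (20% dropout) or 17.0 (20% missed visits). Early visits can go the other way: at Day 8 with 20% missed visits, niclosamide moves from 38.4% to 40.7% and placebo from 20.6% to 22.1%, so the difference widens from 17.8 to 18.6 points.
- **Every non-clearer without a sample is dropped.** This is exact only for never-negative subjects. One with an earlier negative who turned positive again stays in as uncleared.

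The reply does not reach 8.2.6, which has no time-to-event estimate and is not a small group.

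**Conclusion.** The upward bias of the by-visit rows is real and holds even under random missingness. It is already corrected for the Part 2 primary endpoint and for 8.2.2, 8.2.3 and 8.3.6; no planned test or trial conclusion changes.

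What remains is mainly SAP 8.2.6. With true acquisition of 20% and 20% missing, the Day 43 row and the overall row would differ by about 4 points and err in opposite directions. The gap is about 2 points at 10% missing and about 6 at 30%. With about 45 subjects per arm, one subject is 2.2 points, so this is a reporting inconsistency of modest size. For 8.2.1 the point carries little weight.

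These sizes rest on assumed missingness and acquisition rates, on missingness unrelated to outcome, and on the overall row using the Section 4 default. If that row were meant to follow the visit rule, the conflict would vanish but the upward bias would remain.

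**What to change.** - **SAP 8.2.6:** report Kaplan-Meier cumulative percentages through each visit and for the overall row, so that both come from one estimate. State that subjects never positive are censored at their last stool sample, and say how death without a positive sample is handled.
- **SAP 8.2.1:** report counts with a not-assessed count; Kaplan-Meier is optional.
- **By-visit tables in 8.1.1 and the sections that copy the rule:** add a not-assessed count. Treat deaths and hospitalised withdrawals without clearance as not cleared, as in 8.1. Replace the condition of an earlier negative test with sustained clearance as defined there.
- **All-subjects denominator:** do not use it as the point estimate, because under dropout it is more biased than the present rule.

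The cost is SAP wording, table-shell edits and a small amount of extra programming. No new data are needed.

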8.1.2. Sensitivity Analysis

The analysis of the primary efficacy endpoint, time to fecal viral RNA clearance assessed by RT-qPCR, will also be conducted on the PP set.

8.1.3. Subgroup Analysis

The primary efficacy endpoint, time to fecal viral RNA clearance assessed by RT-qPCR, will be analyzed in the same manner as the primary analysis for age group (<65 years, ≥65 years) and gender. For the subgroup analysis of age group, the primary endpoint will be analyzed by the log-rank test and Cox Proportional Hazards model adjusting only for gender. For the subgroup analysis of gender, the primary endpoint will be analyzed by the log-rank test and Cox Proportional Hazards model adjusting only for age group.

8.2. Gastrointestinal Secondary Efficacy Endpoints

The analysis of the gastrointestinal secondary efficacy endpoints will be conducted on the EE set unless otherwise specified.

8.2.1. Time to fecal viral RNA clearance assessed by RT-qPCR (Part 1)

The number of subjects with and without fecal viral RNA clearance assessed by RT-qPCR (as defined in [Section 8.1.](#)) will be summarized up to each post-first dose study visit (Days 4, 8, 15, 22, 29, 36, and 43) by treatment group. For each study visit, only subjects with available assessment at the visit or having a negative stool test before the visit will be included in the summary and counted in the denominator for the percentages.

8.2.2. Time from the first dose of study treatment to the first formed stool

Only subjects with loose or watery stool (Bristol Stool Scale Types 6-7) on Day 1 will be included in this analysis. This data was collected on the Diarrhea Clinical Assessment at Randomization eCRF.

Date of the earliest formed stool (followed by a non-watery stool) between study visits will be collected on the Diarrhea Clinical Assessment eCRF. A summary table will include the number and percentage of subjects achieving and not achieving the first formed stool (followed by a non-watery stool) up to each post-first dose study visit (Days 4, 8, 15, 22, 29, 36, and 43) by treatment group. For each study visit, only subjects with available assessment at the visit or having a formed stool test before the visit will be included in the summary and counted in the denominator for the percentages.

Time to the first formed stool is defined as the time in days from the first dose of study treatment to the first formed stool (followed by a non-watery stool). If subjects experienced a formed stool on the first day of treatment, time to first formed stool will be imputed as 0.5 days. Subjects without a first formed stool will be censored using the same rules as described for the primary efficacy endpoint in [Section 8.1.](#) Time to the first formed stool (followed by a non-watery stool) will be analyzed using the same time to event methods described for the analysis of the primary endpoint in [Section 8.1.1.](#)

8.2.3. Time from the first dose of study treatment to the last watery stool

Only subjects with loose or watery stool (Bristol Stool Scale Types 6-7) on Day 1 will be included in this analysis. This data was collected on the Diarrhea Clinical Assessment at Randomization eCRF.

Date of the last watery stool between study visits will be collected on the Diarrhea Clinical Assessment eCRF. A summary table of events will include the number and percentage of subjects achieving and not achieving the last watery stool (followed by all formed stools) up to each post-first dose study visit (Days 4, 8, 15, 22, 29, 36, and 43) by treatment group. For each study visit, only subjects with available assessment at the visit or having the last watery stool before the visit will be included in the summary and counted in the denominator for the percentages.

Time to the last watery stool is defined as the time in days from the first dose of study treatment to the last watery stool (followed by all formed stools). Only subjects with baseline and at least one non-missing post-baseline will be included. Time to the last loose/watery stool during the course of the study will utilize the last visit at which a subject had watery stool. If a subject did not experience watery stool at any timepoint post-baseline, we impute time as 0.5 days. Subjects will not be censored because relapse cases of watery stool will be included in the analysis (i.e. subject experienced watery stool again after formed stool) and in such cases, the last visit at which relapse occurred is considered to be the last visit at which watery stool is experienced. Time to the last watery stool will be analyzed using the same time to event methods described for the analysis of the primary endpoint in [Section 8.1.1](#).

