10.3 Part 1 Only: Days 2, 3, 5, 6, and 7: Safety Monitoring

- Vital signs (For safety monitoring only. Vital signs do not need to be entered into the CRF, though detected adverse events should be entered in the CRF.)
- AE monitoring
- Concomitant medications

10.4 Days 4 (± 1 day), 8 (± 1 day), and 15 (± 2 day): Treatment

- Changes in the medical history and concomitant medications since previous visit
- Pregnancy test (urine or serum) on Day 15
- Stool sample for the central laboratory
- Clinical assessment of diarrhea (including anti-diarrheal agents) since previous visit
- Nasopharyngeal swab for the central laboratory
- Laboratory assessments:
 - Central: Obtain samples for central laboratory at Day 8 and Day 15.

- Local: Any other laboratory tests may be conducted for the physician's safety assessment according to the local practice and patient's clinical needs.
- Overall clinical assessment
- Continued TID daily dosing
- Daily diary
- AE monitoring
- Concomitant medications

10.5 Days 22 (± 2 days), 29 (± 2 days), 36 (± 3 days), and 43 (± 3 days): Short-Term Follow-Up

The following procedures and tests will be performed at the days noted above or upon early termination if the patient discontinues the study less than 4 weeks after the last dose of study drug.

- Changes in the medical history and concomitant medications since previous visit
- Stool sample for the central laboratory
- Clinical assessment of diarrhea (including anti-diarrheal agents) since previous visit
- Nasopharyngeal swab for the central laboratory
- Laboratory assessments:
 - Central: Obtain samples for central laboratory at Day 29 and 43.
 - Local: Any other laboratory tests may be conducted for the physician's safety assessment according to the local practice and patient's clinical needs.
- Overall clinical assessment
- Daily diary, with diary collection on Day 43
- AE monitoring
- Concomitant medications

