13.3. Unblinding

At the time of the final analysis at Day 43, the randomization will be unblinded to the central study team after the official database lock. However, the investigators, other site study staff, and subjects will remain blinded to their treatment allocation(s) for as long as they are participating in the study.

14. Changes in the Planned Analysis

Bristol Stool Scale Types 5-7 has been updated to 6-7 for the secondary endpoint in section 3.2.2, section 8.2.2, and section 8.2.3 to be consistent with Appendix B of the protocol. Furthermore, for both analyses if the day of the formed stool/last watery stool was the same as the first day of treatment, then the time to event was imputed as 0.5 days. In the time to last watery stool analysis, there was no censoring necessary.

15. References

Sato, T. (1989). On the variance estimator for the Mantel-Haenszel risk difference, *Biometrics* 45, 1323-1324. Letter to the editor.

16. Appendices

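### SAP 8.2.3 gives both a date-based and a visit-based rule for time to last watery stool; read literally, the visit rule moves event times later, by up to 6 days on nominal visit days and up to 12 within the visit windows

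*SAP*

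**What the plan says.** SAP Section 8.2.3 describes the data first: "Date of the last watery stool between study visits will be collected on the Diarrhea Clinical Assessment eCRF". Its definition follows: "Time to the last watery stool is defined as the time in days from the first dose of study treatment to the last watery stool". Both are at the level of the day.

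The same paragraph then gives a rule at the level of the visit: "Time to the last loose/watery stool during the course of the study will utilize the last visit at which a subject had watery stool". Relapse is handled the same way: "the last visit at which relapse occurred is considered to be the last visit at which watery stool is experienced". One imputation is added: "If a subject did not experience watery stool at any timepoint post-baseline, we impute time as 0.5 days".

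SAP Section 14, which lists changes to the planned analysis, applies the 0.5-day value by day: "if the day of the formed stool/last watery stool was the same as the first day of treatment". It also records the change of Bristol types and the absence of censoring. It does not mention replacing a stool date by a visit. Protocol Section 8.2 defines the endpoint to the stool itself.

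The companion endpoint in SAP 8.2.2, first formed stool, also collects a date and is defined to the stool. It has no visit rule.

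**The concern.** Two programmers could follow Section 8.2.3 and obtain different event times for the same subject. One would subtract the first dose date from the recorded stool date; the other would use the visit. The visit rule appears twice, so it is hard to dismiss as a slip, and taken literally it discards day-level information that the study already collects.

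The endpoint receives the time-to-event methods of SAP 8.1.1: a stratified log-rank test, a Cox hazard ratio and Kaplan-Meier medians. It is analysed in the efficacy evaluable set, for which about 60 stool-positive patients are planned, and only in those with Bristol Type 6-7 stool on Day 1. In so small a group, a reported median number of days could reflect the visit schedule as much as the illness.

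**Working it through.** The documents give no rounding size, sample size or power for this endpoint, so there is no plan figure to reproduce.

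**Inputs.** Post-dose visits are on Days 4, 8, 15, 22, 29, 36 and 43 (SAP 8.2.3), with dosing on Day 1. Windows are ±1, ±1, ±2 days for Days 4, 8, 15 (Protocol 10.4) and ±2, ±2, ±3, ±3 days for Days 22, 29, 36, 43 (Protocol 10.5). Those sections make each diarrhea assessment cover the interval back to the preceding visit.

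**Three readings of the visit sentence.**

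1. *The visit at which watery stool was reported supplies the time.* Times move later. Example: a last watery stool on Day 16, reported on Day 22, becomes 22 − 1 = 21 days instead of 16 − 1 = 15, a shift of 6.
2. *Only watery stool on the visit day counts.* Episodes between visits are lost and times are too early. Example: watery on Day 8, last watery stool on Day 14, none on Day 15. The time becomes 8 − 1 = 7 days instead of 14 − 1 = 13.
3. *The visit only identifies which record holds the date.* No shift.

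**Size under reading 1.** For a gap of g days, the maximum shift is g − 1. If stools are spread evenly over the whole days of the interval, the mean shift is (g − 1)/2. A stool on the day of the preceding visit is assigned to that visit. The widest gap takes the preceding visit as early, and the next as late, as the windows allow.

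| Visit | Nominal gap | Max shift | Mean shift | Widest gap | Max shift with windows |
|---|---|---|---|---|---|
| Day 4 | 3 | 2 | 1 | 5 − 1 = 4 | 3 |
| Day 8 | 4 | 3 | 1.5 | 9 − 3 = 6 | 5 |
| Day 15 | 7 | 6 | 3 | 17 − 7 = 10 | 9 |
| Day 22 | 7 | 6 | 3 | 24 − 13 = 11 | 10 |
| Day 29 | 7 | 6 | 3 | 31 − 20 = 11 | 10 |
| Day 36 | 7 | 6 | 3 | 39 − 27 = 12 | 11 |
| Day 43 | 7 | 6 | 3 | 46 − 33 = 13 | 12 |

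Continuous time would give means of 1.5, 2 and 3.5 days, but the eCRF records whole dates, so the whole-day means apply.

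**Boundary case.** Take a last watery stool after dosing on Day 1, reported at the Day 4 visit. Section 14 gives 0.5 days. Reading 1 of Section 8.2.3 gives 4 − 1 = 3 days if that report counts as post-baseline.

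**Effect on the analysis (assumed values only).** Simulation with 15 subjects per arm, exponential times in whole days capped at 42, all counted as events, two-sided unstratified log-rank test at 0.05, 3,000 runs per scenario. Medians are averages over runs, recorded date → reporting visit.

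| Assumed medians (days) | Shorter arm | Longer arm | Mean shift | Power |
|---|---|---|---|---|
| 3 vs 5 | 3.63 → 5.01 | 5.69 → 7.74 | 2.0 | 27.4% → 24.4% |
| 4 vs 7 | 4.71 → 6.44 | 7.83 → 10.55 | 2.2 | 31.0% → 28.9% |
| 6 vs 10 | 6.79 → 9.22 | 11.00 → 14.06 | 2.3 | 28.2% → 26.6% |
| 8 vs 12 | 8.87 → 11.79 | 13.15 → 16.16 | 2.3 | 19.8% → 18.6% |

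Arm medians rise by about 1.4 to 3.1 days, and power falls by about 1 to 3 points. As a check on the test routine, the primary-endpoint assumptions of SAP 4.1 gave 74.3% power at alpha 0.05 (stated 74%) and 84.2% at 0.10 (stated 83%).

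**The case against.** The strongest defence is reading 3. The eCRF asks for a date at each visit, so one subject can have several, and some rule must say which record counts. The last visit with watery stool is a natural choice, and the relapse sentence serves the same purpose. The formal definition and Section 14 fit this reading, and under it nothing is rounded. It remains possible, so a shift cannot be asserted as fact. But the SAP never says that the visit is only a pointer to a date, and the plain wording makes the visit the source of the time.

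Four stronger inferences are not supported:

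- *Durations are certainly overstated.* This holds only under reading 1; reading 2 errs in the opposite direction.
- *Six days is the upper limit.* It is the nominal maximum for weekly gaps. The first two intervals allow less, and the windows allow more.
- *The comparison between arms is biased.* The grid and rule are the same in both arms. If the arms do not differ, the rule creates no difference.
- *The two stool endpoints are made non-comparable, and this is a harm.* They are different events, and the SAP plans no comparison between them.

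It is also fair that this is one of many secondary endpoints, tested at a nominal 0.05 without multiplicity adjustment.

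**Conclusion.** The conflict within SAP 8.2.3, and between it and Section 14, is real and should be resolved. The rule as worded replaces a collected date by a visit. Together with the look-back of the assessments, its literal reading delays the event time by at most 2, 3 or 6 days on nominal days, and by up to 12 with the windows. The mean shifts of 1, 1.5 and 3 days assume stools spread evenly within intervals and no unscheduled visits.

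The consequence is displaced Kaplan-Meier times, more ties and a small loss of power. The simulated sizes rest on assumed medians and an assumed 15 subjects per arm; the documents give neither. The primary endpoint is not affected.

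**What to change.** In SAP 8.2.3, replace the visit-based sentences by one rule: the event time is the latest recorded eCRF date of watery stool across all visits, relapse included, minus the first dose date. State that the visit serves only to find the record, or as a fallback when the date is missing, and report by arm how often the fallback was used. Use one trigger for the 0.5-day value, so that Sections 8.2.3 and 14 agree.

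The cost is a change of SAP wording and one derivation. The date is already collected, so no new data are needed.
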